Mean observation period (days)	XX	xx	XX
Total observation period (days)	XXX	xxx	XXX
Annualized bleeding rate			
n	х	x	х
Mean (SD)	x.xx (x.xx)	x.xx (x.xx)	x.xx (x.xx)
Median	x.xx	X.XX	x.xx
Min ; Max	x.x ; x.x	x.x ; x.x	x.x ; x.x

N: Number of patients in Full Analysis Set (FAS). n: Number of patients with the parameter. SD: Standard Deviation. n\*: Number of bleeds.

Severity: Assessment by investigator.

Cohort 1: AAV5-hFIX 5.0 x 10^12 gc/kg, Cohort 2: AAV5-hFIX 2.0 x 10^13 gc/kg

Only bleeds requiring on demand FIX infusion are included.

Total observation period (yrs) for each cohort is calculated as the sum of the observation periods of all patients in that cohort.

Sponsor: uniQure biopharma B.V	Date 27MAY2021	larix
Trial ID: CT-AMT-060-01 EudraCT No: 2013-00557942-42	Table Shells	Final Version 05 Page 35 of 66

Table 14.2.19 Summary of post treatment bleeding episodes and annualized bleeding rates - Period: From last prophylactic dose to cut-off - Spontaneous and unknown bleeds - FAS

	Cohort 1 (N=x) n (%)	Cohort 2 (N=x) n (%)	Total (N=x) n (%)	
		~ /		
Severity, n*				
Severe	х	х	х	
Mild/Moderate	х	x	х	
Location, n*				
Right - Joint, Elbow	х	х	х	
Right - Joint, Finger(S)	х	х	х	
Right - Joint, Knee	х	х	х	
Right - Joint, Wrist	х	х	Х	
Left - Joint, Elbow	х	х	х	
Continued for left	x	x	х	
Other	х	х	Х	

N: Number of patients in Full Analysis Set (FAS). n: Number of patients with the parameter. SD: Standard Deviation. n\*: Number of bleeds. Severity: Assessment by investigator. Cohort 1: AAV5-hFIX 5.0 x 10^12 gc/kg, Cohort 2: AAV5-hFIX 2.0 x 10^13 gc/kg

Only bleeds requiring on demand FIX infusion are included.

Total observation period (yrs) for each cohort is calculated as the sum of the observation periods of all patients in that cohort.

Sponsor: uniQure biophan	ma B.V		Date 27MAY2021			larix	
Trial ID: CT-AMT-060-01 EudraCT No: 2013-00557	942-42	2 Table Shells				Final Version 05 Page 36 of 66	
Table 14.2.20 Summary of CCL domains and total scores - FAS							
	Coh	ort 1 (N = x)	Coh	Cohort 2 (N = x)		Total $(N = x)$	
	Absolute value	Change from Baseline	Absolute value	Change from Baseline	Absolute value	Change from Baseline	
PF (Physical Functioning	g)						
Visit 1							
n	х		х		х		
Mean (SD)	xx.xx (xx.xx)		xx.xx (xx.xx)		xx.xx (xx.xx)		
Median	xx.xx		xx.xx		XX.XX		
Min ; Max	xx.x ; xx.x		xx.x ; xx.x		xx.x ; xx.x		
Visit 21							
n	х	х	х	x	х	х	
Mean (SD)	xx.xx (xx.xx)	xx.xx (xx.xx)	xx.xx (xx.xx)	xx.xx (xx.xx)	xx.xx (xx.xx)	xx.xx (xx.xx)	
Median	XX.XX	xx.xx	XX.XX	xx.xx	XX.XX	XX.XX	
Min ; Max	xx.x ; xx.x	xx.x ; xx.x	xx.x ; xx.x	xx.x ; xx.x	xx.x ; xx.x	xx.x ; xx.x	
Visit 23							
n	х	х	х	х	х	х	
Mean (SD)	xx.xx (xx.xx)	xx.xx (xx.xx)	xx.xx (xx.xx)	xx.xx (xx.xx)	xx.xx (xx.xx)	xx.xx (xx.xx)	
Median	xx.xx	xx.xx	XX.XX	xx.xx	xx.xx	XX.XX	
Min ; Max	xx.x ; xx.x	xx.x ; xx.x	xx.x ; xx.x	xx.x ; xx.x	xx.x ; xx.x	xx.x ; xx.x	

N: Number of patients in Full Analysis Set (FAS). n: Number of patients with the parameter. SD: Standard Deviation.

Cohort 1: AAV5-hFIX 5.0 x 10^12 gc/kg, Cohort 2: AAV5-hFIX 2.0 x 10^13 gc/kg

Data collected at additional visits will be presented in listings.
Sponsor: uniQure biopharma B.V	Date 27MAY2021	larix
Trial ID: CT-AMT-060-01 EudraCT No: 2013-00557942-42	Table Shells	Final Version 05 Page 37 of 66

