# Statistical analyses and presentation of data

# 4.1 General Considerations

All reporting will be made for the Full Analysis Set. Reporting may also be made for other analysis populations (PP Analysis Set), or subgroups of patients based on for example genotype.

Data will be presented in tables and listings following the principles in ICH E3 guideline regarding (structure and content of clinical reports). On the listings, cohort will appear in a separate column and the listings will be sorted by cohort/dose and patient ID within cohort/dose. In the tables data from each cohort/dose will be presented in separate columns. For selected endpoints data will also be presented graphically.

All data will be listed, including unused and spurious data. Imputation of missing or partial data will not be done unless explicitly described. In the case of imputation of missing data, both the original missing or partial data and the imputed values will be listed. Continuous data will be shown in listings with the same precision as captured.

Summary tables will show the number of non-missing values

Numerical data will be presented in summary tables by number of patients, arithmetic mean, median, standard deviation, minimum and maximum and CV (%). Categorical data will be presented by number and percent of patients as well as the number of events (where applicable).

Patient level summaries (listings) will be presented adjusted for observation time where applicable. This includes but is not limited to the annualized rate of selected signs and symptoms and annualized bleeding rate.

In general, laboratory parameters will be presented by visit and will include categorization of parameters into low/normal/high where applicable. For some of the laboratory parameters a measurement of '< x' (x being a numerical value) are occasionally registered. In such a case a value equal to  $0.5^*x$  is used when summary tables are generated, whereas the '< x' will be reported in listings. This recalculation for use in summary tables will also be documented in the ADRG.

The distance in days between a measurement/event and the trial drug administration date is calculated as follows:

- If date(measurement/event) < date(trial drug administration): Distance in days = date(measurement/event) – date(trial drug administration)
- If date(measurement/event) >= date(trial drug administration): Distance in days = date(measurement/event) – date(trial drug administration) + 1

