## 4.4.2.3 Prophylactic and On-demand FIX Replacement Therapy

As mentioned in section 4.3.4.3 administration on demand FIX replacement therapy in the 1 year period prior to screening has been registered. All these data will be listed. The on-demand FIX replacement therapy products used and the total dose used will be summarised for each cohort for this 1 year period prior to screening.

From Visit 1 and throughout the entire trial participation period, patients have been asked to document use of FIX replacement therapy in an e-diary. Two different modules in the e-diary will be used for registering prophylactic and on-demand FIX replacement therapy respectively.

The patient e-diary modules will include questions with respect to

- Date/time of administration
- Drug name
- Dose

All data will be presented in listings. The listings will be split two parts: a) the period from screening and until the end of tapering b) the period from end of tapering until end of trial/cut-off date in an interim analysis.

The use of prophylaxis and on-demand treatment in general will be summarized according to product and type (on-demand or prophylaxis). The summarises will be performed by cohort and overall. Furthermore, the total on-demand use for each patient (regardless of product) for the post tapering period will be summarized by cohort. The total dose for each patient will be annualized i.e. the dose will be adjusted for the length of the observation time (end of tapering until end of trial/cut-off date in an interim analysis) for the patient in question.

A listing will be generated combining on a patient level the information for the 1-year period prior to screening and for the post tapering-period including on-demand FIX-replacement therapy (annualized), bleeding episodes and annualized bleeding rates.

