# 7 Tables, Listings and Figures

The shell listings, tables, and figures generated appear in the two shell documents (CT\_AMT\_060\_01\_Table\_Shells\_v05.docx and CT\_AMT\_060\_01\_Listing\_Shells\_v05.docx) attached to this SAP. The two documents are considered as being a part of this SAP.

Larix A/S - Strictly Confidential F501-0-1–5 SAP Template Page 30 of 34

Date: 27MAY2021

CT-AMT-060-01 EudraCT No.: 2013-005579-42

Statistical Analysis Plan

Final no. 05 Page 31 of 34

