N: Number of patients in Full Analysis Set (FAS). n: Number of patients with at least one dose of medication. Cohort 1: AAV5-hFIX 5.0 x 10^12 gc/kg, Cohort 2: AAV5-hFIX 2.0 x 10^13 gc/kg

Sponsor: uniQure biopharma B.V		Date 27MAY2021		larix
Trial ID: CT-AMT-060-01 EudraCT No: 2013-00557942-42		Table Shells		Final Version 05 Page 19 of 66
Table 14.2.7 Summary of post-treatment	t use of FIX replace	ment therapy - On-Dema	and - Period: From Dosing To cut	-off - FAS
	Cohort 1 (N=x)	Cohort 2 (N=x)	Total (N=x)	
Use of on-demand FIX replacement therapy	n (%)	n (%)	n (%)	
Any medication	x (xx.x)	x (xx.x)	x (xx.x)	
Benefix	x (xx.x)	x (xx.x)	x (xx.x)	
Haemonine	x (xx.x)	x (xx.x)	x (xx.x)	
Mononine	x (xx.x)	x (xx.x)	x (xx.x)	
Etc.				
Repeat for all medications reported				

N: Number of patients in Full Analysis Set (FAS). n: Number of patients with at least one dose of medication. Cohort 1: AAV5-hFIX 5.0 x 10^12 gc/kg, Cohort 2: AAV5-hFIX 2.0 x 10^13 gc/kg

Sponsor: uniQure biopharma B.V		Date 27MAY2021		larix
Trial ID: CT-AMT-060-01 EudraCT No: 2013-00557942-42		Table Shells		Final Version 05 Page 20 of 66
Table 14.2.8 Summary o	f FIX replacement therapy d	lose - Period: One year prior t	o screening - FAS	
	Cohort 1 (N=x)	Cohort 2 (N=x)	Total (N=x)	
FIX Infusions (IU/year)				
n	x	x	x	
Mean (SD)	xxx (xxx)	xxx (xxx)	xxx (xxx)	
Median	XXX	XXX	XXX	
Min ; Max	xxx ; xxx	xxx ; xxx	xxx ; xxx	

N: Number of patients in Full Analysis Set (FAS). n: Number of patients with at least one dose of medication. Cohort 1: AAV5-hFIX 5.0 x 10^12 gc/kg, Cohort 2: AAV5-hFIX 2.0 x 10^13 gc/kg FIX infusions is the total sum of FIX administrated as prophylaxis and On-demand.

Sponsor: uniQure biopharma B.V		Date 27MAY2021		larix
Trial ID: CT-AMT-060-01 EudraCT No: 2013-00557942-42		Table Shells		Final Version 05 Page 21 of 66
Table 14.2.9 Summary of	FIX replacement therapy d	lose - Period: From tapering-o	ff to cut-off - FAS	
	Cohort 1 (N=x)	Cohort 2 (N=x)	Total (N=x)	
Annualized FIX Infusions (IU/yea	r)			
n	х	x	х	
Mean (SD)	xxx (xxx)	xxx (xxx)	xxx (xxx)	
Median	XXX	XXX	XXX	
Min ; Max	xxx ; xxx	xxx ; xxx	xxx ; xxx	

N: Number of patients in Full Analysis Set (FAS). n: Number of patients with at least one dose of medication. Cohort 1: AAV5-hFIX 5.0 x 10^12 gc/kg, Cohort 2: AAV5-hFIX 2.0 x 10^13 gc/kg FIX infusions is the total sum of FIX administrated as prophylaxis and On-demand.

Sponsor: uniQure biopharma B.V	Date 27MAY2021			larix

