Trial ID: CT-AMT-060-01 EudraCT No: 2013-00557942-42	Та	able Shells		Final Version 05 Page 22 of 66
Table 14.2.10 Summary of bleeding episode	s and annualized bleedin	g rates - All bleeds - Per	iod: One year prior to screening - FAS	6
	Cohort 1 (N=x) n (%)	Cohort 2 (N=x) n (%)	Total (N=x) n (%)	
Number of patients with bleed, n (%)	x (xx.x)	x (xx.x)	x (xx.x)	
Number of bleeds	x	x	x	
Bleeds per patient (min; max)	x; x	x; x	x; x	
Annualized bleeding rate				
n	х	х	x	
Mean (SD)	x.xx (x.xx)	x.xx (x.xx)	x.xx (x.xx)	
Median	x.xx	x.xx	X.XX	
Min ; Max	x.x; x.x	x.x; x.x	x.x; x.x	

N: Number of patients in Full Analysis Set (FAS). n: Number of patients with the parameter. SD: Standard Deviation. n\*: Number of bleeds. Severity: Assessment by investigator.

Cohort 1: AAV5-hFIX 5.0 x 10^12 gc/kg, Cohort 2: AAV5-hFIX 2.0 x 10^13 gc/kg

Only bleeds requiring on demand FIX infusion are included.

Sponsor: uniQure biopharma B.V	Date		larix	
Trial ID: CT-AMT-060-01 EudraCT No: 2013-00557942-42	Та	ble Shells		Final Version 05 Page 23 of 66
Table 14.2.11 Summary of bleeding episodes	and annualized bleeding	g rates - Spontaneous ble	eeds - Period: One year prior to screen	ing - FAS
_	Cohort 1 (N=x) n (%)	Cohort 2 (N=x) n (%)	Total (N=x) n (%)	
Number of patients with bleed, n (%)	x (xx.x)	x (xx.x)	x (xx.x)	
Number of bleeds	х	х	х	
Bleeds per patient (min; max)	x; x	x; x	x; x	
Annualized bleeding rate				
n	х	х	x	
Mean (SD)	x.xx (x.xx)	x.xx (x.xx)	x.xx (x.xx)	
Median	X.XX	x.xx	X.XX	
Min ; Max	x.x; x.x	x.x; x.x	x.x; x.x	

N: Number of patients in Full Analysis Set (FAS). n: Number of patients with the parameter. SD: Standard Deviation. n\*: Number of bleeds. Severity: Assessment by investigator.

Cohort 1: AAV5-hFIX 5.0 x 10^12 gc/kg, Cohort 2: AAV5-hFIX 2.0 x 10^13 gc/kg

Only bleeds requiring on demand FIX infusion are included.

Sponsor: uniQure biopharma B.V	Date 27MAY2021			larix
Trial ID: CT-AMT-060-01 EudraCT No: 2013-00557942-42	Та	ble Shells		Final Version 05 Page 24 of 66
Table 14.2.12 Summary of bleeding episodes	and annualized bleeding	g rates - Traumatic bleed	ds - Period: One year prior to screening	- FAS
	Cohort 1 (N=x) n (%)	Cohort 2 (N=x) n (%)	Total (N=x) n (%)	
Number of natients with bleed n (%)	x (xx x)	x (xx x)	x (xx x)	
Number of bleeds	X	X	x	
Bleeds per patient (min; max)	x; x	x; x	x; x	
Annualized bleeding rate				
n	х	х	x	
Mean (SD)	x.xx (x.xx)	x.xx (x.xx)	x.xx (x.xx)	
Median	x.xx	x.xx	X.XX	
Min ; Max	x.x; x.x	x.x; x.x	x.x; x.x	

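### Table shells 14.2.8 and 14.2.9 define n for FIX use in IU/year as users only, so read literally non-users drop out instead of counting as 0; and SAP 4.4.2.3 and the shells disagree on on-demand versus total dose (minor)

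*SAP*

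**What the plan says.** Table shells 14.2.8 (year before screening) and 14.2.9 (tapering-off to cut-off) each show n, mean (SD), median and minimum/maximum of FIX infusions in IU/year. Under both, the footnote reads "n: Number of patients with at least one dose of medication", and a second footnote fixes the content: "FIX infusions is the total sum of FIX administrated as prophylaxis and On-demand". SAP Section 7 gives the shell documents full standing: "The two documents are considered as being a part of this SAP".

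The SAP text differs on both matters.

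- **Who is summarised.** Section 4.1: "All reporting will be made for the Full Analysis Set" and "Summary tables will show the number of non-missing values". Section 4.4.2.3: "The total dose for each patient will be annualized i.e. the dose will be adjusted for the length of the observation time".
- **Which dose.** Section 4.4.2.3 states that "the total on-demand use for each patient (regardless of product) for the post tapering period will be summarized by cohort". Its sentence on the year before screening also reads most naturally as on-demand dose, though less explicitly.

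The supportive endpoint (Protocol 8.2.2 and the SAP list of endpoints) is total FIX consumption. SAP Section 6, which lists deviations from the protocol analysis, names only the change from 72 hours to 10 days for therapy-free FIX activity.

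**The concern.** No FIX use is a valid value of 0 IU/year, and after tapering it is the outcome of most interest. A table that summarises users only leaves out the subjects who did best. In cohorts of about five, one or two such subjects change the mean materially, and a cohort with no use at all would show n=0 and blanks where the answer is 0.

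The dose content matters for a similar reason. One programmer working from Section 4.4.2.3 and another working from the shell footnote could report different totals for the same subjects, and only the shell definition matches the endpoint.

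**Working it through.** The plan gives no figure on this point, so there is nothing to reproduce. The check compares the texts and sizes each difference.

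**1. Definition of n.** The same footnote stands under Tables 14.2.5 to 14.2.7. It fits there, because those tables count users of each product. It does not fit a summary of a continuous quantity. The bleeding-rate shells, from Table 14.2.10 on, use another pattern: a separate row for patients with a bleed, and "n: Number of patients with the parameter".

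If k of N subjects are non-users, the sum of IU/year is the same either way and only the divisor changes:

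users-only mean ÷ all-subject mean = N/(N−k)

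| N | k=1 | k=2 | k=3 | k=4 | k=5 |
|---|---|---|---|---|---|
| 5 (planned cohort) | 5/4 = 1.25 | 5/3 = 1.67 | 5/2 = 2.5 | 5/1 = 5 | blank |
| 7 (most allowed in Cohort 2, Protocol 9.1) | 7/6 = 1.17 | 7/5 = 1.4 | 7/4 = 1.75 | 7/3 = 2.33 | 7/2 = 3.5 |

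For k = 3 or 4 of 5 the all-subject median is 0, while a users-only table shows a positive value.

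Invented values for illustration, not trial data: 0, 0, 10,000, 20,000 and 30,000 IU/year.

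- All five subjects: mean 12,000, SD 13,038, median 10,000, minimum 0.
- Three users: mean 20,000, SD 10,000, median 20,000, minimum 10,000. The ratio is 20,000/12,000 = 5/3.
- Against an assumed prior-year mean of 40,000, the reduction reads 1 − 20,000/40,000 = 50% instead of 1 − 12,000/40,000 = 70%.

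**2. Who can be a non-user.**

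- *Table 14.2.9.* SAP 4.4.2.2 starts the period on the date of the last prophylactic dose. If that dose is counted, every subject tapered off prophylaxis has at least one dose. Only subjects on on-demand therapy at entry can then be non-users, and n may be close to N. If it is not counted, the ratios above can apply to anyone. The SAP does not say which.
- *Table 14.2.8.* Protocol 9.2 requires prophylaxis or on-demand therapy at entry, so on total dose few prior-year non-users are expected. On an on-demand definition, prophylaxis subjects with no treated bleed that year would drop out.

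**3. On-demand versus total dose.** Protocol 6.2 gives a background regimen of 40 U/kg two to three times a week. It is used here as an assumption.

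- *Table 14.2.8.* Prophylaxis all year amounts to 40 × 2 × 52 = 4,160 to 40 × 3 × 52 = 6,240 IU/kg/year. The shell counts this and an on-demand total does not.
- *Table 14.2.9, start-date dose only.* Assume 10 to 40 U/kg (25% to 100% of 40) given at week 8 to 14, with follow-up to week 260. The period is (260−8) × 7/365.25 = 4.83 years to (260−14) × 7/365.25 = 4.71 years. The dose adds 10/4.83 = 2.1 to 40/4.71 = 8.5 IU/kg/year.
- *Table 14.2.9, later prophylaxis.* Protocol 11.4 allows prophylaxis to restart, and Table 5-4 (footnote 4), 10.3.1 and 12.1.3 foresee continuous prophylaxis in long-term follow-up. A subject on the background regimen for some share of the period would add that share of 4,160 to 6,240 IU/kg/year. The share is unknown. It also depends on the start dates in SAP Appendix 2, which is not visible in the public copy.

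**The case against.** The footnote only labels a printed count; no sentence says that non-users are excluded from the mean or median. The table titles say FAS, Section 4.1 puts all reporting on the FAS, and Section 4.4.2.3 annualizes the dose for each patient. Carry-over from Tables 14.2.5 to 14.2.7 is the simplest explanation. This stands as far as intent goes: a reader might infer that the tables were in fact run without zeros, and the documents do not show that. What remains is that n sits directly above the statistics it would describe, the shells are part of the SAP, and no text says that non-use is entered as 0.

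Section 4.4.2.3 is also not confined to on-demand: it plans a general summary of both types of use by product. That is true, but its explicit post-tapering dose sentence is on-demand only.

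The practical effect is small. N is printed beside n, Listings 16.2.6.8 and 16.2.6.12 give subject-level use, no hypothesis is tested, and the error would run against the product. All of this stands and sets the severity.

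**Conclusion.** Wrong as written, and minor. The shells define n in a way that, followed literally, removes non-users, against SAP 4.1 and 4.4.2.3. The two parts of the SAP also give different dose definitions, and Section 6 does not declare the difference.

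For a cohort of five the literal reading inflates the mean 1.25 to 5 times for one to four non-users. For subjects tapered off prophylaxis in Table 14.2.9, this holds only if the start-date dose is not counted. Three further inferences go too far:

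- That the N/(N−k) ratios and the start-date addition of 2.1 to 8.5 IU/kg/year both apply to the same previously prophylactic subject. Counting the start-date dose makes that subject a user.
- That the dose definition matters only in Table 14.2.8. Restarted or continuous prophylaxis could matter much more in Table 14.2.9 than the start-date dose, and it cannot be sized.
- That Table 14.2.8 is unaffected by the definition of n. That is roughly so only under the total-dose definition.

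The IU/kg figures rest on the background regimen, not on trial data.

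**What to change.** - In both tables, summarise all FAS subjects with an observation period, enter non-users as 0 IU/year, and define n accordingly. Show the number of users in a separate row, as the bleeding shells do for patients with a bleed.
- Align SAP 4.4.2.3 with the shells on total consumption for both periods. On-demand use may be kept as an additional row.
- State whether the dose on the period start date and any restarted prophylaxis are counted in Table 14.2.9.
- Have the sponsor state how prior-year prophylaxis IU in Table 14.2.8 is obtained. SAP 4.3.4.2 collects dose, frequency and months on prophylaxis, and 4.3.4.3 records FIX per bleed, but no text says how a total is built from them.

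The cost is SAP and shell wording plus a small amount of programming. No new data are needed for the zeros or the user counts. One drawback remains: the prior-year total may be less precise than the diary-based total after tapering, so the two periods are not strictly comparable.

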14.3.1 Displays of Adverse Events

Sponsor: uniQure biopharma B.V	Date 27	MAY2021	a	irix
Trial ID: CT-AMT-060-01 EudraCT No: 2013-00557942-42	Table	Shells	Final V Page	ersion 05 38 of 66
Table 14.3.1.1 Overall Summary of Treatme	ent Emergent Adverse Event	s - FAS		
	Cohort 1 (N=x) n (%) E	Cohort 2 (N=x) n (%) E	Total (N=x) n (%) E	
All TEAEs	x (xx.x) x	x (xx.x) x	x (xx.x) x	
Mild TEAEs	x (xx.x) x	x (xx.x) x	x (xx.x) x	
Moderate TEAEs	x (xx.x) x	x (xx.x) x	x (xx.x) x	
Severe TEAEs	x (xx.x) x	x (xx.x) x	x (xx.x) x	
Probably Related TEAEs (ADRs)	x (xx.x) x	x (xx.x) x	x (xx.x) x	
Possibly Related TEAEs (ADRs)	x (xx.x) x	x (xx.x) x	x (xx.x) x	
Unlikely Related TEAEs (ADRs)	x (xx.x) x	x (xx.x) x	x (xx.x) x	
Serious TEAEs (SAEs)	x (xx.x) x	x (xx.x) x	x (xx.x) x	
Deaths	x (xx.x) x	x (xx.x) x	x (xx.x) x	
TEAEs leading to discontinuation	x (xx.x) x	x (xx.x) x	x (xx.x) x	
TEAEs for special notification	x (xx.x) x	x (xx.x) x	x (xx.x) x	

TEAE: Treatment Emergent Adverse Event. ADR. Adverse Drug Reaction.

N: Number of patients in Full Analysis Set (FAS). n: Number of patients with events. (%): Percentage of patients in FAS with Adverse Event. E: Number of Adverse Events.

Cohort 1: AAV5-hFIX 5.0 x 10^12 gc/kg, Cohort 2: AAV5-hFIX 2.0 x 10^13 gc/kg

Sponsor: uniQure biopharma B.V	Date 27MAY2021			arix
Trial ID: CT-AMT-060-01	Table Shells			Final Version 05
Eddrac 1 No. 2013-00337942-42				Fage 39 01 00
Table 14.3.1.2 Frequency and Incidence of TEAEs b	y MedDRA SOC and PT - FAS			
SOC PT	Cohort 1 (N=x) n (%) E	Cohort 2 (N=x) n (%) E	Total (N=x) n (%) E	
Any TEAEs	x (xx.x) x	x (xx.x) x	x (xx.x) x	
Musculoskeletal and connective tissue disorders	x (xx.x) x	x (xx.x) x	x (xx.x) x	
Arthralgia	x (xx.x) x	x (xx.x) x	x (xx.x) x	
Musculoskeletal pain	x (xx.x) x	x (xx.x) x	x (xx.x) x	
Back pain	x (xx.x) x	x (xx.x) x	x (xx.x) x	
Pain in extremity	x (xx.x) x	x (xx.x) x	x (xx.x) x	
Neck pain	x (xx.x) x	x (xx.x) x	x (xx.x) x	
Joint swelling	x (xx.x) x	x (xx.x) x	x (xx.x) x	
Tenosynovitis	x (xx.x) x	x (xx.x) x	x (xx.x) x	
Infections and infestations	x (xx.x) x	x (xx.x) x	x (xx.x) x	
Nasopharyngitis	x (xx.x) x	x (xx.x) x	x (xx.x) x	
Sinusitis	x (xx.x) x	x (xx.x) x	x (xx.x) x	
Influenza	x (xx.x) x	x (xx.x) x	x (xx.x) x	
Rhinitis	x (xx.x) x	x (xx.x) x	x (xx.x) x	
	x (xx.x) x	x (xx.x) x	x (xx.x) x	
	x (xx.x) x	x (xx.x) x	x (xx.x) x	
	x (xx.x) x	x (xx.x) x	x (xx.x) x	
	x (xx.x) x	x (xx.x) x	x (xx.x) x	
	x (xx.x) x	x (xx.x) x	x (xx.x) x	

TEAE: Treatment Emergent Adverse Event. MedDRA: Medical Dictionary for Regulatory Activities. SOC: System Organ Class. PT: Preferred Term.

N: Number of patients in Full Analysis Set (FAS). n: Number of patients with events. (%): Percentage of patients in FAS with Adverse Event. E: Number of Adverse Events. Cohort 1: AAV5-hFIX 5.0 x 10^12 gc/kg, Cohort 2: AAV5-hFIX 2.0 x 10^13 gc/kg

Adverse Events coded with MedDRA version 17.1

Sponsor: uniQure biopharma B.V	Date 27MAY2021			larix
Trial ID: CT-AMT-060-01	Table Shalls			Final Version 05
Table 14.3.1.3 Frequency and Incidence of Related TEA	AEs by MedDRA SOC and PT - F	AS		Page 40 of 66
SOC PT	Cohort 1 (N=x) n (%) E	Cohort 2 (N=x) n (%) E	Total (N=x) n (%) E	
Any Related TEAEs	x (xx.x) x	x (xx.x) x	x (xx.x) x	
Investigations Hepatic enzyme increased Transaminases increased	x (xx.x) x x (xx.x) x x (xx.x) x	x (xx.x) x x (xx.x) x x (xx.x) x	x (xx.x) x x (xx.x) x x (xx.x) x	
Alanine aminotransferase increased	x (xx.x) x	x (xx.x) x	x (xx.x) x	
General disorders and administration site conditions Pyrexia Drug ineffective	x (xx.x) x x (xx.x) x x (xx.x) x	x (xx.x) x x (xx.x) x x (xx.x) x	x (xx.x) x x (xx.x) x x (xx.x) x	
Psychiatric disorders	x (xx.x) x	x (xx.x) x	x (xx.x) x	
Anxiety	x (xx.x) x	x (xx.x) x	x (xx.x) x	
Reproductive system and breast disorders Prostatitis	x (xx.x) x x (xx.x) x	x (xx.x) x x (xx.x) x	x (xx.x) x x (xx.x) x	
Skin and subcutaneous tissue disorders	x (xx.x) x	x (xx.x) x	x (xx.x) x	
Rash	x (xx.x) x	x (xx.x) x	x (xx.x) x	
Cardiac disorders Palpitations	x (xx.x) x x (xx.x) x	x (xx.x) x x (xx.x) x	x (xx.x) x x (xx.x) x	

FAS: Full Analysis Set. TEAE: Treatment Emergent Adverse Event. MedDRA: Medical Dictionary for Regulatory Activities (version 17.1). SOC: System Organ Class. PT: Preferred Term. N: Number of patients in FAS. n: Number of patients with events. (%): Percentage of patients in Full Analysis Set with Adverse Event. E: Number of Adverse Events. Cohort 1: AAV5-hFIX 5.0 x 10^12 gc/kg, Cohort 2: AAV5-hFIX 2.0 x 10^13 gc/kg

Sponsor: uniQure biopharma B.V	Date 27MAY2021			larix
Trial ID: CT-AMT-060-01 EudraCT No: 2013-00557942-42	Table Shells			Final Version 05 Page 41 of 66
Table 14.3.1.3 Frequency and Incidence of Related TEAEs by MedDRA SOC and I	PT – FAS			
System Organ Class Preferred Term	Cohort 1 (N=x) n (%) E	Cohort 2 (N=x) n (%) E	Total (N=x) n (%) E	
Nervous system disorders	x (xx.x) x	x (xx.x) x	x (xx.x) x	
Headache	x (xx.x) x	x (xx.x) x	x (xx.x) x	
Cardiac disorders	x (xx.x) x	x (xx.x) x	x (xx.x) x	
Palpitations	x (xx.x) x	x (xx.x) x	x (xx.x) x	
Musculoskeletal and connective tissue disorders	x (xx.x) x	x (xx.x) x	x (xx.x) x	
Joint swelling	x (xx.x) x	x (xx.x) x	x (xx.x) x	
Skin and subcutaneous tissue disorders	x (xx.x) x	x (xx.x) x	x (xx.x) x	
Rash	x (xx.x) x	x (xx.x) x	x (xx.x) x	

TEAE: Treatment Emergent Adverse Event. MedDRA: Medical Dictionary for Regulatory Activities. SOC: System Organ Class. PT: Preferred Term.

N: Number of patients in Full Analysis Set (FAS). n: Number of patients with events. (%): Percentage of patients in FAS with Adverse Event. E: Number of Adverse Events.

Cohort 1: AAV5-hFIX 5.0 x 10^12 gc/kg, Cohort 2: AAV5-hFIX 2.0 x 10^13 gc/kg

Adverse Events coded with MedDRA version 17.1

Events classified as Possibly Related or Probably Related are included in output.

Sponsor: uniQure biopharma B.V

Date 27MAY2021

Trial ID: CT-AMT-060-01 EudraCT No: 2013-00557942-42

Table Shells

Table 14.3.1.4 Frequency and Incidence of Deaths by MedDRA SOC and PT - FAS

As 14.3.1.3

Sponsor: uniQure biopharma B.V	Date 27MAY2021			larix
Trial ID: CT-AMT-060-01 EudraCT No: 2013-00557942-42	Table Shells			Final Version 05 Page 43 of 66
Table 14.3.1.5 Frequency and Incidence of Serious TEAE	s by MedDRA SOC and PT - F	FAS		
SOC PT	Cohort 1 (N=x) n (%) E	Cohort 2 (N=x) n (%) E	Total (N=x) n (%) E	
Any Serious TEAEs	x (x.xx) x	x (x.xx) x	x (x.xx) x	
Investigations Hepatic enzyme increased	x (x.xx) x x (x.xx) x	x (x.xx) x x (x.xx) x	x (x.xx) x x (x.xx) x	
Alanine aminofransferase increased	x (x.xx) x	x (x.xx) x	x (x.xx) x	
General disorders and administration site conditions Pyrexia	x (x.xx) x x (x.xx) x	x (x.xx) x x (x.xx) x	x (x.xx) x x (x.xx) x	
Nervous system disorders Myelopathy	x (x.xx) x x (x.xx) x	x (x.xx) x x (x.xx) x	x (x.xx) x x (x.xx) x	

TEAE: Treatment Emergent Adverse Event. MedDRA: Medical Dictionary for Regulatory Activities. SOC: System Organ Class. PT: Preferred Term.

N: Number of patients in Full Analysis Set (FAS). n: Number of patients with events. (%): Percentage of patients in FAS with Adverse Event. E: Number of Adverse Events.

Cohort 1: AAV5-hFIX 5.0 x 10^12 gc/kg, Cohort 2: AAV5-hFIX 2.0 x 10^13 gc/kg

Adverse Events coded with MedDRA version 17.1

Sponsor: uniQure biopharma B.V	Date 27MAY2021			arix
Trial ID: CT-AMT-060-01 EudraCT No: 2013-00557942-42	Table Shells			Final Version 05 Page 44 of 66
Table 14.3.1.6 Frequency and Incidence of TEAEs of N	Mild Severity by MedDRA SOC as	nd PT - Full analysis	s set	
SOC PT	Cohort 1 (N=x) n (%) E	Cohort 2 (N=x) n (%) E	Total (N=x) n (%) E	
Any mild TEAEs	x (x.xx) x	x (x.xx) x	x (x.xx) x	
Infections and infestations Nasopharvneitis	x (x.xx) x	x (x.xx) x	x (x.xx) x	
Eye infection	x (x.xx) x	x (x.xx) x	x (x.xx) x	
Influenza	x (x.xx) x	x (x.xx) x	x (x.xx) x	
Sinusitis	x (x.xx) x	x (x.xx) x	x (x.xx) x	
Respiratory tract infection	x (x.xx) x	x (x.xx) x	x (x.xx) x	
Rhinitis	x (x.xx) x	x (x.xx) x	x (x.xx) x	
Oral herpes	x (x.xx) x	x (x.xx) x	x (x.xx) x	
Musculoskeletal and connective tissue disorders	x (x.xx) x	x (x.xx) x	x (x.xx) x	
Arthralgia	x (x.xx) x	x (x.xx) x	x (x.xx) x	
Back pain	x (x.xx) x	x (x.xx) x	x (x.xx) x	
Joint swelling	x (x.xx) x	x (x.xx) x	x (x.xx) x	
Groin pain	x (x.xx) x	X (X.XX) X	x (x.xx) x	
Tenosynovitis	x (x.xx) x	X (X.XX) X	x (x.xx) x	
Pain in extremity	x (x.xx) X	x (x.xx) x	x (x.xx) x	
Neck pain	x (x.xx) X	x (x.xx) x	x (x.xx) x	
F	x (x.xx) x	x (x.xx) x	x (x.xx) x	

TEAE: Treatment Emergent Adverse Event. MedDRA: Medical Dictionary for Regulatory Activities. SOC: System Organ Class. PT: Preferred Term.

N: Number of patients in Full Analysis Set (FAS). n: Number of patients with events. (%): Percentage of patients in FAS with Adverse Event. E: Number of Adverse Events. Cohort 1: AAV5-hFIX 5.0 x 10^12 gc/kg, Cohort 2: AAV5-hFIX 2.0 x 10^13 gc/kg

Adverse Events coded with MedDRA version 17.1

	arix
Trial ID: CT-AMT-060-01         Table Shells           EudraCT No: 2013-00557942-42         Table Shells	Final Version 05 Page 45 of 66

Table 14.3.1.6 Frequency and Incidence of TEAEs of Mild Severity by MedDRA SOC and PT - Full analysis set

SOC PT	Cohort 1 (N=x) n (%) E	Cohort 2 (N=x) n (%) E	Total (N=x) n (%) E	
Nervous system disorders	x (x.xx) x	x (x.xx) x	x (x.xx) x	
Headache	x (x.xx) x	x (x.xx) x	x (x.xx) x	
Dizziness	x (x.xx) x	x (x.xx) x	x (x.xx) x	
Nervous system disorder	x (x.xx) x	x (x.xx) x	x (x.xx) x	
Hypoaesthesia	x (x.xx) x	x (x.xx) x	x (x.xx) x	
General disorders and administration site conditions	x (x.xx) x	x (x.xx) x	x (x.xx) x	
Pyrexia	x (x.xx) x	x (x.xx) x	x (x.xx) x	
Influenza like illness	x (x.xx) x	x (x.xx) x	x (x.xx) x	
Peripheral swelling	x (x.xx) x	x (x.xx) x	x (x.xx) x	
Investigations	x (x.xx) x	x (x.xx) x	x (x.xx) x	
Hepatic enzyme increased	x (x.xx) x	x (x.xx) x	x (x.xx) x	
Transaminases increased	x (x.xx) x	x (x.xx) x	x (x.xx) x	
Platelet count decreased	x (x.xx) x	x (x.xx) x	x (x.xx) x	
Alanine aminotransferase increased	x (x.xx) x	x (x.xx) x	x (x.xx) x	
Psychiatric disorders	x (x.xx) x	x (x.xx) x	x (x.xx) x	
Sleep disorder	x (x.xx) x	x (x.xx) x	x (x.xx) x	
Anxiety	x (x.xx) x	x (x.xx) x	x (x.xx) x	

TEAE: Treatment Emergent Adverse Event. MedDRA: Medical Dictionary for Regulatory Activities. SOC: System Organ Class. PT: Preferred Term.

N: Number of patients in Full Analysis Set (FAS). n: Number of patients with events. (%): Percentage of patients in FAS with Adverse Event. E: Number of Adverse Events. Cohort 1: AAV5-hFIX 5.0 x 10^12 gc/kg, Cohort 2: AAV5-hFIX 2.0 x 10^13 gc/kg

Adverse Events coded with MedDRA version 17.1

Sponsor: uniQure biopharma B.V	Date 27MAY2021	larix
Trial ID: CT-AMT-060-01 EudraCT No: 2013-00557942-42	Table Shells	Final Version 05 Page 46 of 66

Table 14.3.1.6 Frequency and Incidence of TEAEs of Mild Severity by MedDRA SOC and PT - Full analysis set

SOC PT	Cohort 1 (N=x) n (%) E	Cohort 2 (N=x) n (%) E	Total (N=x) n (%) E	
Gastrointestinal disorders	x (x.xx) x	x (x.xx) x	x (x.xx) x	
Abdominal pain lower	x (x.xx) x	x (x.xx) x	x (x.xx) x	
Diarrhoea	x (x.xx) x	x (x.xx) x	x (x.xx) x	
Irritable bowel syndrome	x (x.xx) x	x (x.xx) x	x (x.xx) x	
Dyspepsia	x (x.xx) x	x (x.xx) x	x (x.xx) x	
Injury, poisoning and procedural complications	x (x.xx) x	x (x.xx) x	x (x.xx) x	
Ulna fracture	x (x.xx) x	x (x.xx) x	x (x.xx) x	
Joint injury	x (x.xx) x	x (x.xx) x	x (x.xx) x	
Abdominal injury	x (x.xx) x	x (x.xx) x	x (x.xx) x	
Tooth fracture	x (x.xx) x	x (x.xx) x	x (x.xx) x	
Cardiac disorders	x (x.xx) x	x (x.xx) x	x (x.xx) x	
Tachycardia	x (x.xx) x	x (x.xx) x	x (x.xx) x	
Palpitations	x (x.xx) x	x (x.xx) x	x (x.xx) x	
Skin and subcutaneous tissue disorders	x (x.xx) x	x (x.xx) x	x (x.xx) x	
Actinic keratosis	x (x.xx) x	x (x.xx) x	x (x.xx) x	
Rash	x (x.xx) x	x (x.xx) x	x (x.xx) x	
Vascular disorders	x (x.xx) x	x (x.xx) x	x (x.xx) x	

TEAE: Treatment Emergent Adverse Event. MedDRA: Medical Dictionary for Regulatory Activities. SOC: System Organ Class. PT: Preferred Term.

N: Number of patients in Full Analysis Set (FAS). n: Number of patients with events. (%): Percentage of patients in FAS with Adverse Event. E: Number of Adverse Events. Cohort 1: AAV5-hFIX 5.0 x 10^12 gc/kg, Cohort 2: AAV5-hFIX 2.0 x 10^13 gc/kg

Adverse Events coded with MedDRA version 17.1

Sponsor: uniQure biopharma B.V	Date 27MAY2021			larix
Trial ID: CT-AMT-060-01	Table Shelle			Final Version 05
EudraCT No: 2013-00337942-42	Table Shells			Page 47 of 66
Table 14.3.1.6 Frequency and Incidence of TEAEs of Mild Severity by	MedDRA SOC and PT - Full analysis set			
	Cohort 1	Cohort 2	Total	
SOC PT	(N=x) n (%) E	(N=x) n (%) E	(N=x) n (%) E	
Haematoma	x (x.xx) x	x (x.xx) x	x (x.xx) x	
Reproductive system and breast disorders	x (x.xx) x	x (x.xx) x	x (x.xx) x	
Prostatitis	x (x.xx) x	x (x.xx) x	x (x.xx) x	
Ear and labyrinth disorders	x (x.xx) x	x (x.xx) x	x (x.xx) x	
Cerumen impaction	x (x.xx) x	x (x.xx) x	x (x.xx) x	
Immune system disorders	x (x.xx) x	x (x.xx) x	x (x.xx) x	
Hypersensitivity	x (x xx) x	x (x xx) x	x (x xx) x	
	X (XAA) X	A (AIAA) A	A (A.AA) A	
Renal and urinary disorders	x (x.xx) x	x (x.xx) x	x (x.xx) x	
Renal colic	x (x.xx) x	x (x.xx) x	x (x.xx) x	
Blood and lymphatic system disorders	x (x.xx) x	x (x.xx) x	x (x.xx) x	
Splenomegaly	x (x.xx) x	x (x.xx) x	x (x.xx) x	
Eve disorders	x (x xx) y	x (x xx) x	x (x xx) x	
Blepharitis	x (x,xx) x	x (x xx) x	x (x.xx) x	
	A (A.AA) A	A (A.AA) A	A (A.AA) A	
Respiratory, thoracic and mediastinal disorders	x (x.xx) x	x (x.xx) x	x (x.xx) x	

TEAE: Treatment Emergent Adverse Event. MedDRA: Medical Dictionary for Regulatory Activities. SOC: System Organ Class. PT: Preferred Term.

N: Number of patients in Full Analysis Set (FAS). n: Number of patients with events. (%): Percentage of patients in FAS with Adverse Event. E: Number of Adverse Events. Cohort 1: AAV5-hFIX 5.0 x 10^12 gc/kg, Cohort 2: AAV5-hFIX 2.0 x 10^13 gc/kg

Adverse Events coded with MedDRA version 17.1

Sponsor: uniQure biopharma B.V	Date 27MAY2021	larix
Trial ID: CT-AMT-060-01 EudraCT No: 2013-00557942-42	Table Shells	Final Version 05 Page 48 of 66

Table 14.3.1.6 Frequency and Incidence of TEAEs of Mild Severity by MedDRA SOC and PT - Full analysis set

SOC PT	Cohort 1 (N=x) n (%) E	Cohort 2 (N=x) n (%) E	Total (N=x) n (%) E	
Chronic obstructive pulmonary disease	x (x.xx) x	x (x.xx) x	x (x.xx) x	

TEAE: Treatment Emergent Adverse Event. MedDRA: Medical Dictionary for Regulatory Activities. SOC: System Organ Class. PT: Preferred Term.

N: Number of patients in Full Analysis Set (FAS). n: Number of patients with events. (%): Percentage of patients in FAS with Adverse Event. E: Number of Adverse Events. Cohort 1: AAV5-hFIX 5.0 x 10^12 gc/kg, Cohort 2: AAV5-hFIX 2.0 x 10^13 gc/kg

Adverse Events coded with MedDRA version 17.1

Sponsor: uniQure biopharma B.V	Date 27MAY2021			arix
Trial ID: CT-AMT-060-01 EudraCT No: 2013-00557942-42	Table Shells			Final Version 05 Page 49 of 66
Table 14.3.1.7 Frequency and Incidence of TEAEs of M	loderate Severity by MedDRA Second	OC and PT - Full and	alysis set	
SOC PT	Cohort 1 (N=x) n (%) E	Cohort 2 (N=x) n (%) E	Total (N=x) n (%) E	
Any moderate TEAEs	x (x.xx) x	x (x.xx) x	x (x.xx) x	
Infections and infestations Pulpitis dental	x (x.xx) x x (x xx) x	x (x.xx) x	x (x.xx) x	
Bronchitis	x (x.xx) x	x (x.xx) x	x (x.xx) x	
Cellulitis	x (x.xx) x	x (x.xx) x	x (x.xx) x	
Musculoskeletal and connective tissue disorders Musculoskeletal stiffness	x (x.xx) x x (x.yx) x	x (x.xx) x	x (x.xx) x	
Back pain	x (x.xx) x x (x.xx) x	x (x.xx) x	x (x.xx) x	
Arthralgia	x (x.xx) x	x (x.xx) x	x (x.xx) x	
Injury, poisoning and procedural complications Muscle strain Upper limb fracture	x (x.xx) x x (x.xx) x x (x.xx) x	x (x.xx) x x (x.xx) x x (x.xx) x	x (x.xx) x x (x.xx) x x (x.xx) x	
General disorders and administration site conditions Drug ineffective Pyrexia	x (x.xx) x x (x.xx) x x (x.xx) x	x (x.xx) x x (x.xx) x x (x.xx) x	x (x.xx) x x (x.xx) x x (x.xx) x	
Psychiatric disorders	x (x.xx) x	x (x.xx) x	x (x.xx) x	

TEAE: Treatment Emergent Adverse Event. MedDRA: Medical Dictionary for Regulatory Activities. SOC: System Organ Class. PT: Preferred Term.

N: Number of patients in Full Analysis Set (FAS). n: Number of patients with events. (%): Percentage of patients in FAS with Adverse Event. E: Number of Adverse Events. Cohort 1: AAV5-hFIX 5.0 x 10^12 gc/kg, Cohort 2: AAV5-hFIX 2.0 x 10^13 gc/kg

Adverse Events coded with MedDRA version 17.1

Nervous system disorder

Sponsor: uniQure biopharma B.V	Date 27MAY2021			larix
Trial ID: CT-AMT-060-01 EudraCT No: 2013-00557942-42	Table Shells			Final Version 05 Page 50 of 66
Table 14.3.1.7 Frequency and Incidence of TEAEs of Moderate	Severity by MedDRA SOC and PT - Full analysis set			
SOC PT	Cohort 1 (N=x) n (%) E	Cohort 2 (N=x) n (%) E	Total (N=x) n (%) E	
Anxiety	x (x.xx) x	x (x.xx) x	x (x.xx) x	
Nervous system disorders	x (x.xx) x	x (x.xx) x	x (x.xx) x	

x (x.xx) x

TEAE: Treatment Emergent Adverse Event. MedDRA: Medical Dictionary for Regulatory Activities. SOC: System Organ Class. PT: Preferred Term.

N: Number of patients in Full Analysis Set (FAS). n: Number of patients with events. (%): Percentage of patients in FAS with Adverse Event. E: Number of Adverse Events.

